6.8.1 Hematologic toxicity

Management of neutropenia and thrombocytopenia

Neutropenia and thrombocytopenia are recognized common adverse drug reactions reported for both olaparib and cediranib. Treatment should be managed according to Table 9:

Table 9 Management of neutropenia or thrombocytopenia

	Olaparib dose	Cediranib dose
CTCAE Grade 1-2	Investigator judgement to continue treatment or allow dose interruption; dose interruptions should be for a maximum of 3 weeks; appropriate supportive treatment and causality investigation	Investigator judgement to continue treatment or allow dose interruption; dose interruptions should be for a maximum of 3 weeks; appropriate supportive treatment and causality investigation
ANC >1.0 G/L or Platelet count >50 G/L		

Table 9 Management of neutropenia or thrombocytopenia

	Olaparib dose	Cediranib dose
CTCAE grade 3-4 ANC <1.0 G/L or Platelet count <50 G/L	Dose interruption until recovered to CTCAE Grade ≤1 for a maximum of 3 weeks. Upon recovery, olaparib dose should be reduced by one dose level. If repeat CTCAE Grade 3-4 occurrence, further dose reduce one or both IPs	Dose interruption until recovered to CTCAE Grade ≤1 for a maximum of 3 weeks. Upon recovery, cediranib dose should be reduced by one dose level. If repeat CTCAE Grade 3-4 occurrence, further dose reduce one or both IPs

Abbreviations: ANC absolute neutrophil count; CTCAE common terminology criteria for adverse events; IP investigational product

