6.8.1.2 Dose modifications for hematologic toxicity

Patients who have IPs held for hematologic toxicities should have blood counts and differentials checked at least weekly until recovery; these data should be recorded in eCRF as extra laboratory examinations. If counts do not improve to CTCAE Grade 1 or better despite drug cessation for 3 weeks, patients should be referred to a hematologist for further assessment. A bone marrow analysis should be considered per hematology assessment.

For AEs that are unrelated to the study drug, study drug may be withheld for up to 3 weeks at the discretion of the treating Investigator.

Management of anemia

Anemia is a common adverse drug reaction related to olaparib. Cediranib is not reported to increase the risk of anemia. Management of anemia is in accordance with Table 10:

Table 10 Management of anaemia

	Olaparib dose	Cediranib dose
Hb <10 but \geq 8 g/dL	
Give appropriate supportive treatment and investigate causality.
 
Investigator judgement to continue olaparib or interrupt dose for a maximum of 3 weeks.
 
If repeat Hb <10 but \geq8 g/dL, dose interrupt until Hb \geq10 g/dL for maximum of 3 weeks and upon recovery dose reduce to 150 mg bd as a first step and to 100 mg bd as a second step
	No change
Hb < 8 g/dL	
Give appropriate supportive treatment and investigate causality.
 
Interrupt olaparib until improved to Hb \geq10 g/dL.
 
Upon recovery dose reduce olaparib to 150 mg bd
	No change

Abbreviations: bd twice daily; Hb hemoglobin

Common treatable causes of anemia (eg, iron, vitamin B12 or folate deficiencies and hypothyroidism) should be investigated and appropriately managed. In some cases, management of anemia may require blood transfusions. Any subsequently required dose interruptions, related to development of anemia, or coexistent with newly developed neutropenia, and/or thrombocytopenia, will require olaparib dose reductions to 150 mg twice daily as a first step and to 100 mg twice daily as a second step.

If Hb drops to < 8 g/dL despite the dose reduction or more than one blood transfusion is required to recover Hb levels with no alternative explanation for the anemia, olaparib should be permanently discontinued.

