6.8.1.3 Management of prolonged hematological toxicities while on study treatment

If a patient develops prolonged hematological toxicity such as:

- \geq 2 week interruption/delay in olaparib due to CTCAE Grade 3 or worse anemia and/or development of blood transfusion dependence
- \geq 2 week interruption/delay in 1 or both IPs due to CTCAE Grade \geq 3 neutropenia (ANC <1 x 10⁹/L)
- \geq 2 week interruption/delay in 1 or both IPs due to CTCAE Grade \geq 3 thrombocytopenia and/or development of platelet transfusion dependence (Platelets <50 x 10⁹/L)

Check weekly differential blood counts including reticulocytes and peripheral blood smear. If any blood parameters remain clinically abnormal after 3 weeks of dose interruption, the patient should be referred to hematologist for further investigations. Bone marrow analysis

and/or blood cytogenetic analysis should be considered at this stage according to standard hematological practice. Both IPs should be discontinued if blood counts do not recover to CTCAE Grade ≤ 1 within 3 weeks of dose interruption.

Development of a confirmed myelodysplastic syndrome (MDS) or other clonal blood disorder should be reported as an SAE and full reports must be provided by the investigator to AstraZeneca Patient Safety. Olaparib treatment should be discontinued if patient's diagnosis of MDS and/or acute myeloid leukemia (AML) is confirmed.

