6.8.2 Non-hematologic toxicity

Cediranib should be discontinued should any of the following AEs occur: GI perforation; arterial thromboembolic events; PRES (radiologically confirmed); severe or medically significant hemorrhage and severe persistent hypertension despite maximal anti-hypertensive treatment.

Dose modifications for other non-hematologic events on IPs should be managed according to Table 11.

Table 11 General Management of Non-Hematologic Toxicity

Observation	Action
AE resolves promptly with supportive care	Maintain dose level
Any \geq Grade 3 non-hematologic (excluding grade 3 fatigue or easily correctable asymptomatic grade 3 laboratory abnormalities)	Hold IP(s) ^a for up to 3 weeks until toxicity resolves to \leq Grade 1. Treatment may be restarted at one dose level lower for the IP(s) causing the toxicity (see Table 7 and Table 8), at the treating investigator's discretion ^b . Reoccurrence of Grade 3 or 4 toxicity would require dose reduction of both IPs.
Any grade 2 non-hematologic AE or grade 3 fatigue related to cediranib or olaparib that persists despite maximal support.	Hold IP(s) ^a for up to 3 weeks until toxicity resolves to Grade ≥ 1 . Treatment may be restarted at one dose level lower for the IP(s) causing the toxicity (see Table 7 and Table 8), at the treating investigator's discretion ^b .
Grade 3 or 4 non-hematologic AE related to cediranib and olaparib combination that does not resolve to Grade 0-2 within 3 weeks despite maximum supportive care after treating patient at the lowest reduced dose level ^c	Discontinue IP(s)

a. At the discretion of the investigator, one IP may be held or dose modified or discontinued independently if the observed toxicity is attributed to only one of the drugs, while the patient continued to receive the second drug not associated with the observed toxicity. The time a given drug is held should not exceed 3 weeks.

- b. Patients who are at the lowest reduced dose level may have their drug resumed at that dose level after discussion with the AstraZeneca Study Physician and the Principal Investigator if evidence of clinical benefit.
- c. For venous thromboembolic events, treatment may be resumed at the discretion of the investigator once patient is asymptomatic (Section 6.7.3.11).

Abbreviations: AE adverse event; IP investigational product(s)

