
Recurrent or persistent (>24 hours) or symptomatic increase by >20 mmHg (diastolic) or to > 140/90 mmHg if previously within normal limits.
 
Monotherapy may be indicated
	
Initiate BP medication for first line treatment. Suggestions: ACE inhibitor or Calcium Channel Blocker
 
Escalate dose of medication in step wise fashion until BP is controlled or at a maximum dose
 
If BP is not controlled to <140/90 mmHg with one “maximized” drug regimen, then add a second agent.
 
Study drug does not need to be held unless otherwise clinically necessary
 
Consider renal consult
	
Increase frequency of monitoring until stabilized to BP <140/90 mmHg
	
Do not withhold cediranib unless otherwise clinically necessary

Table 12 Hypertension Monitoring and Management

Event	Antihypertensive Therapy	Blood Pressure Monitoring	Cediranib Dose Modification
Requiring more than one drug or more intensive therapy than previously.	
Maximize 2 drug regimen
 
Suggestions: ACE-inhibitor + Calcium Channel Blocker
 
Escalate doses of existing medication until BP is controlled or at a maximum dose.
 
If BP is not controlled to <140/90 mmHg with two drug regimen, then add a third agent.
 
Study Drug will not be held during trial of two drug combinations. Additional antihypertensive drugs, up to a total of 4, may be maximized for BP control.
 
Consider consult with a BP management specialist if greater than 3 drugs are required for BP control.
	Increase frequency of monitoring until stabilized to BP <140/90 mmHg	
Do not withhold cediranib unless BP is not decreased to less than 150/100 mmHg 48 hours after multi-drug therapy is instituted or if clinical symptoms worsen (eg, headache).
 
If BP is not controlled to less than 150/100 mmHg with maximal therapy or if clinical symptoms worsen, then withhold cediranib (up to 3 weeks) until maximum effect of the antihypertensive agents is achieved.
 
If BP is reduced to Grade 1 within 3 weeks, cediranib may be resumed at prior dose.

Table 12 Hypertension Monitoring and Management

Event	Antihypertensive Therapy	Blood Pressure Monitoring	Cediranib Dose Modification

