If threatening consequences OR SBP \geq 180mmHg OR DBP \geq 110mmHg	Initiate treatment Hospitalize patient for ICU management, IV therapy as necessary. 14 days are allowed to maximize the full effect of anti-hypertensive agents.	Intensive BP monitoring (hospitalization if necessary)	Withhold cediranib. If BP is reduced to Grade 1 within 3 weeks, cediranib may be resumed at a reduced dose after discussion with the AstraZeneca Study Physician and the Principal Investigator.

Abbreviations: ACE Angiotensin Converting Enzyme; BP blood pressure; DBP diastolic blood pressure; ICU intensive care unit; IV intravenous; SBP systolic blood pressure.

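### Table 11 row 3 of the protocol prints Grade ≥1 as the level that ends a dose hold; every comparable level in Section 6.8 is grade 1 or below, so the sign is reversed

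*Protocol*

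**What the plan says.** Table 11 in protocol Section 6.8.2 sets the general rules for holding and restarting treatment after non-hematologic toxicity. Two of its rows matter here.

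- **Row 2** covers events of grade 3 or higher, "excluding grade 3 fatigue or easily correctable asymptomatic grade 3 laboratory abnormalities". The hold lasts up to 3 weeks and ends at ≤ Grade 1.
- **Row 3** covers "Any grade 2 non-hematologic AE or grade 3 fatigue related to cediranib or olaparib that persists despite maximal support". The drug or drugs are held "for up to 3 weeks until toxicity resolves to Grade" ≥1. Treatment may then restart one dose level lower for the drug causing the toxicity, at the treating investigator's discretion.

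Elsewhere in Section 6.8, Table 9 (grade 3-4 neutropenia or thrombocytopenia) reads "Dose interruption until recovered to CTCAE Grade" ≤1 in both the olaparib and the cediranib cell. Table 12 (hypertension) gives the level in words in two rows: "If BP is reduced to Grade 1 within 3 weeks, cediranib may be resumed at prior dose", and for the most severe category "If BP is reduced to Grade 1 within 3 weeks, cediranib may be resumed at a reduced dose".

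**The concern.** A level that ends a hold should be one the patient does not yet meet when the hold begins and does meet on recovery. Row 3 as printed fails on both counts.

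Row 3 is an operative dosing rule, and no other rule fully replaces it. Row 2 has a sensible level but does not govern row 3 events: it starts at grade 3 and excludes grade 3 fatigue. Section 6.8.3.3 has its own restart rule for fatigue, but for cediranib only, tied to symptoms improving and without a grade. For fatigue attributed to olaparib, and for grade 2 events without their own section, row 3 is the only grade-based restart level.

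A site that follows the text could restart a patient whose grade 2 event or grade 3 fatigue has not improved, and would not be deviating from the protocol. A site that infers the intent would wait for grade 1 or below. With approximately 40 sites planned, the two readings could coexist. Sections 4.5 and 9.3 also keep the dose-modification rules in force for patients who stay on treatment after the Final Protocol Visit.

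**Working it through.** No formula applies. The check has three steps.

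**1. Test the printed level against the grades involved.**

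| Grade | Role in row 3 | Meets ≥1 (printed)? | Meets ≤1? |
|---|---|---|---|
| 3 | starts the hold (fatigue) | yes | no |
| 2 | starts the hold (other events) | yes | no |
| 1 | nearly recovered | yes | yes |
| 0 | fully recovered | no | yes |

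Under ≥1 the hold ends as soon as it begins, and a fully recovered patient never qualifies to restart. Under ≤1 the hold ends at grade 0 or 1, below both trigger grades.

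**2. List every grade-based level in Section 6.8 that ends a hold.**

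| Place | Level |
|---|---|
| Table 9, olaparib cell | ≤1 |
| Table 9, cediranib cell | ≤1 |
| Table 11, row 2 | ≤1 |
| Table 12, hypertension needing more than one drug | grade 1, in words |
| Table 12, most severe hypertension row | grade 1, in words |
| Table 11, row 3 | ≥1 as printed |

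Five of the six are grade 1 or below; only row 3 points the other way.

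**3. Look at the thresholds left out of that count.**

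- Section 6.8.1.2 refers the patient to a hematologist "If counts do not improve to CTCAE Grade 1 or better despite drug cessation for 3 weeks". This is a non-recovery level, written in words, and it agrees with the five.
- Section 6.8.1.3 says "Both IPs should be discontinued if blood counts do not recover to CTCAE Grade" ≤1 within 3 weeks. It also agrees. Adding both gives seven levels on one side (5 + 2 = 7) and row 3 alone on the other.
- Table 11 row 4 uses grade 0-2, but it decides permanent discontinuation at the lowest dose. It does not end a hold and is not a counter-example.
- Table 10 (hemoglobin), Table 13 (free of diarrhea), Table 14 (protein:creatinine ratio and creatinine), Table 16 (ejection fraction) and Section 6.8.3.3 (symptoms) do not use a grade to end a hold.

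Three of the agreeing places (two Table 12 rows and Section 6.8.1.2) use words and no sign, so the intended level does not depend on how one symbol was read. No text in the protocol explains a different direction for row 3.

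**The case against.** The strongest objection is that the finding rests on one sign in a table read from PDF by a program, and that program garbled other text, including some running headers. The agreement among the other levels shows what was intended, but it cannot separate a typing error in the protocol from a misread character, since both would leave the same pattern. This stands as a caveat. Against it, row 2 of the same table carries both a ≥ and a ≤ sign, each in a sensible place, and no second reversed sign was found.

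The count of five is also less independent than it looks. The two Table 9 cells repeat one sentence for a hematologic toxicity, and the two Table 12 rows concern hypertension and cediranib only. Row 2 of Table 11 is the one general non-hematologic comparator. That is fair, but all the comparators agree, and the logical failure in step 1 does not depend on the count.

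Finally, the verb in row 3 implies improvement, the row above shows the pattern, restart is discretionary and at a lower dose, the hold is capped at 3 weeks, and several expected toxicities have their own guidance. All of this reduces the practical risk. It does not supply the missing recovery threshold: discretion over whether to restart is a different thing from a stated level of recovery. The error is better described as a drafting slip than as a design decision.

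**Conclusion.** The point holds. As supplied, row 3 of Table 11 states a restart level that cannot work as a rule, and the level evidently meant is grade 1 or below. As printed, no improvement in grade is needed before restart; as intended, recovery to grade 1 or below is needed within a hold of up to 3 weeks.

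The consequence is an avoidable ambiguity in a safety threshold, which should be corrected. It has no bearing on the objective response rate, the sample size or any other stated figure.

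How many patients would fall under row 3 cannot be derived from the documents. The only related figure is in Section 1.1.4.3: grade 3 or 4 fatigue in 27% of the combination arm of the earlier phase II study. That study enrolled platinum-sensitive patients and used olaparib capsules, and row 3 needs fatigue that persists despite maximal support. The figure shows that the row is not a remote case, but it does not size the problem.

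Confidence is medium, because the conclusion assumes that the sign in the source PDF is the one supplied here.

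**What to change.** Check Table 11 row 3 in the source PDF. If it shows ≥, change the level to Grade ≤1, matching row 2 and Table 9. No other row or section needs to change.

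The cost is one character in one table row. It adds no procedures or visits and alters no other dosing rule, endpoint or analysis.

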All patients should have recurrent platinum-resistant disease, defined as disease recurrence within 6 months (182 days) of the last receipt of platinum-based chemotherapy.

Duration of treatment

There is no maximum duration for taking the study treatments (cediranib + olaparib). Patients should continue on study treatments until:

- Objective radiological disease progression, as defined by RECIST version 1.1 guidelines,
- Unacceptable toxicity,
- Patient withdrawal of consent, or patient meets any other discontinuation criteria.
- Severe non-compliance with the protocol

Both study treatments (cediranib and olaparib) should be discontinued at the same time; patients are not allowed to remain in the study if they are taking either cediranib or olaparib as monotherapy. However, in rare circumstances, patients experiencing ongoing clinical benefit who develop one of the toxicities listed below related to one of the investigational products (IPs) that prevents them to continue to take this IP, may be allowed to continue on the unrelated drug if in the opinion of the treating investigator the risk benefit remains favorable and only after discussion with AstraZeneca Study Physician and the Principal Investigator.

AEs requiring cediranib to be discontinued:

- Gastrointestinal (GI) perforation
- Arterial Thromboembolic Event
- Reversible Posterior Encephalopathy Syndrome (PRES)
- Severe hemorrhage
- Severe persistent hypertension despite maximal anti-hypertensive treatment

AEs requiring olaparib to be discontinued:

- Bone marrow findings consistent with myelodysplastic syndrome (MDS)/acute myeloid leukemia (AML)
- Severe persistent anemia
- Pneumonitis

Once a patient discontinues both cediranib and olaparib, other treatment options are at the discretion of the investigator.

Following discontinuation of study treatment patients will be followed for disease progression by RECIST 1.1 (if they have not already progressed), survival and post-progression anti-cancer therapies until the data cut-off for the primary analysis, approximately 8 months after the last patient has received her first dose of IP. This primary analysis is the final analysis for the study.

Investigational products, dosage and mode of administration

Cediranib

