3.9 Discontinuation of investigational product

Patients may be discontinued from IPs in the following situations:

- Patient decision; the patient is at any time free to discontinue treatment, without prejudice to further treatment. A patient who discontinues treatment is normally expected to continue to participate in the study unless she specifically withdraws her consent to further participation in any study procedures and assessments (see Section 3.10.1).
- Adverse Event (AE), including AEs that meet criteria for discontinuation as defined in Section 6.7; any AEs that, in the opinion of the Investigator or AstraZeneca, contraindicates further dosing.
- Objective progression according to RECIST version 1.1 criteria.
 - Severe non-compliance with the protocol

Both IPs (cediranib and olaparib) should be discontinued at the same time; patients are not allowed to remain in the study if they are taking either cediranib or olaparib as monotherapy.

However, in rare circumstances, patients experiencing ongoing clinical benefit but who develop one of the toxicities listed below, related to one of the IPs, that prevents them to continue to take this IP, may be allowed to continue on the unrelated drug if in the opinion of the treating investigator the risk benefit remains favorable and only after discussion with the AstraZeneca Study Physician and the Principal Investigator.

AEs requiring cediranib to be discontinued:

- GI perforation
- Arterial Thromboembolic Event
- Reversible Posterior Encephalopathy Syndrome (PRES)
- Severe hemorrhage
- Severe persistent hypertension despite maximal anti-hypertensive treatment

AEs requiring olaparib to be discontinued:

- Bone marrow findings consistent with MDS/AML.
- Severe persistent anemia
- Pneumonitis

Refer to Section 6.7 for more information on the management of IP-related toxicities.

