6.8 Management of IP related toxicities

The dose levels and the general approach to dose modification of the cediranib and olaparib component of the combination therapy are shown in Table 7 and Table 8, respectively. Specific dose modification information for some AEs are provided in Section 6.8.3 and Section 6.8.4. Please refer to the current IBs for emerging safety data for cediranib and olaparib: CCI

AEs should be treated with the appropriate maximum supportive care, and dose reductions should be clearly documented in the eCRF.

Table 7 Dose modification cediranib

Dose Level	Cediranib tablets
Initial dose	30 mg daily
Dose reduction 1	20 mg daily
Dose reduction 2	15 mg daily

Table 8 Dose modification of olaparib

Dose Level	Olaparib tablets
Initial dose	200 mg twice daily
Dose reduction 1	150 mg twice daily
Dose reduction 2	100 mg twice daily

At the discretion of the investigator, the study drugs may be held or dose modified independently if the observed toxicity is attributed to only one of the drugs, while the patient continues to receive the drug not associated with the observed toxicity. The time a given drug is held should not exceed 3 weeks. Once dose of study drug(s) have been reduced, no dose re-escalation is permitted.

If treatment has to discontinue due to toxicity, both IPs (cediranib and olaparib) should be discontinued at the same time; patients are not allowed to remain in the study if they are taking either cediranib or olaparib as monotherapy. However, in rare circumstances, patients experiencing ongoing clinical benefit but who develop one of the toxicities listed below related to one of the IPs that prevents them to continue to take this IP, may be allowed to continue on the unrelated drug if in the opinion of the treating investigator the risk benefit remains favorable and only after discussion with the AstraZeneca Study Physician and the Principal Investigator.

AEs requiring cediranib to be discontinued:

- GI perforation
- Arterial Thromboembolic Event
- PRES
- Severe hemorrhage
- Severe persistent hypertension despite maximal anti-hypertensive treatment

AEs requiring olaparib to be discontinued:

- Bone marrow findings consistent with MDS/ AML
- Severe persistent anemia
- Pneumonitis

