Patients experiencing ongoing clinical benefit who experience a related AE where continuation of one of the drugs is considered, in the judgment of the treating Investigator AND the Principal Investigator, to be potentially life threatening or with the potential for long-term harm to the patient, may be allowed to continue on the unrelated drug after discussion with the AstraZeneca Study Physician and the Principal Investigator.

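### Table 11 footnote a lets the investigator alone stop one drug for good and continue the other, contradicting the stop-both rule in the synopsis and Sections 3.9 and 6.8

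*Protocol*

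**What the plan says.** Table 11 (Protocol Section 6.8.2) covers non-hematologic events other than the five that oblige cediranib to stop. Two of its rows call for a hold of up to 3 weeks, and both carry marker a. Footnote a says that, at the investigator's discretion, "one IP may be held or dose modified or discontinued independently if the observed toxicity is attributed to only one of the drugs", while the second drug goes on. It sets no clinical-benefit condition and no consultation. The final row, on discontinuation, carries marker c instead. It covers Grade 3 or 4 events related to the combination that do not settle "within 3 weeks despite maximum supportive care after treating patient at the lowest reduced dose level". Footnote b does name a consultation: patients already at the lowest dose "may have their drug resumed at that dose level after discussion with the AstraZeneca Study Physician and the Principal Investigator".

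Section 6.8, the parent section, has a sentence parallel to footnote a: "the study drugs may be held or dose modified independently if the observed toxicity is attributed to only one of the drugs". Permanent stopping is not in it. The next paragraph says "If treatment has to discontinue due to toxicity, both IPs (cediranib and olaparib) should be discontinued at the same time" and bars staying in the study on one drug. There are two exceptions.

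- **First exception** (synopsis, 3.9 and 6.8): one of eight listed events, five for cediranib and three for olaparib, in rare circumstances. It needs ongoing clinical benefit, a risk-benefit balance the treating investigator still considers favorable, and discussion with the sponsor's study physician and the Principal Investigator.
- **Second exception** (6.8 only): patients with ongoing benefit and a related event where the Principal Investigator and the treating physician both consider going on with one drug "to be potentially life threatening or with the potential for long-term harm to the patient, may be allowed to continue on the unrelated drug", again after that discussion.

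Section 3.9 says "Both IPs (cediranib and olaparib) should be discontinued at the same time". The synopsis, under duration of treatment, says "Both study treatments (cediranib and olaparib) should be discontinued at the same time; patients are not allowed to remain in the study" on either drug alone. Both give the first exception only.

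**The concern.** Footnote a adds to the investigator's sole discretion the one step that Section 6.8 withholds from it. A site managing a toxicity from Table 11 could keep a patient on one drug. A site working from Section 3.9 or 6.8 would stop both, or would first speak to the sponsor's study physician and the Principal Investigator.

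The rule decides whether a patient remains on a single agent in a study of the combination, and whether anyone besides the treating investigator weighs that choice. The protocol itself describes single-agent activity in this population as limited (Section 1.2: olaparib 4%, 1/26; cediranib 17% in one study and 0/35 in another). There is no Data Monitoring Committee (Section 1.5.2), so the discussion is a real part of oversight. Section 4.5 carries the dose-modification and stopping criteria past the Final Protocol Visit, so the conflict continues there.

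**Working it through.** No arithmetic applies and the plan gives no figure to reproduce. The check is to put one case through each rule.

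**Case.** An unlisted Grade 3 non-hematologic event is attributed to cediranib alone. Cediranib is held, the 3 weeks run out, and the event has not resolved.

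**Step 1: does the discontinuation row of Table 11 settle it?** No. That row needs an event related to the combination and a patient treated at the lowest dose level. An event attributed to one drug fails the first condition at any dose, and a patient above the lowest dose fails the second as well.

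**Step 2: what is left in Table 11?** Only footnote a speaks of permanently stopping one drug when toxicity is attributed to that drug.

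**Step 3: compare the answers to whether the patient may stop cediranib and continue olaparib.** The last two columns assume ongoing clinical benefit.

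| Source | Benefit and discussion required? | Event not judged life threatening or lastingly harmful | Event so judged by both investigators |
|---|---|---|---|
| Table 11 footnote a | Neither | Yes, investigator alone | Yes, investigator alone |
| Section 6.8 | Both | No, both drugs stop | Yes, after the discussion |
| Section 3.9 and synopsis | Both, listed events only | No, both drugs stop | No, the second exception is absent |

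Footnote a differs from the other sources in both columns. Section 6.8 also differs from Section 3.9 and the synopsis in the last column, because the second exception was not carried across.

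**Step 4: is there a rule of precedence?** None was found. No text says that Table 11 overrides Sections 3.9 and 6.8 or yields to them.

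**The case against.** The best defense reads the passages together. Table 11 sits inside Section 6.8, so the parent section could be taken to set when a patient may stay on one drug, with footnote a saying only which drug to act on. The marker is on hold rows and the footnote ends with the 3-week limit on a hold, so the extra words look like a drafting slip. Section 3.9 also sends readers to the toxicity-management section. Much of this is fair, and a slip is quite possible. But the footnote still grants discontinuation at the investigator's discretion, and reading it in harmony means ignoring those words.

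Silence elsewhere is weak evidence. Several subsections name a single-drug stop without repeating the condition, some for listed events (GI perforation, arterial thromboembolism) and some for unlisted ones (fistula, venous thromboembolism, severe renal impairment). A reader might infer that the discussion is waived in all of them. The documents do not support that: those subsections say when to stop a drug, not whether the other may continue. Section 6.8.3.1 on hypertension does not help either side, since it asks for discussion in one sentence and orders a permanent stop without it in the next. The finding therefore rests on footnote a, which does address continuing the other drug.

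A reader might also infer that the discussion must come before the harmful drug is stopped. It need not. In Section 6.8 it is a condition for continuing the unrelated drug.

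**Conclusion.** The contradiction stands and can be read directly from the current text. It is an internal inconsistency in a treatment rule, of minor severity.

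Its size in patients cannot be estimated. A reader might multiply the Grade 3 or 4 fatigue (27%) and diarrhea (23%) rates in Section 1.1.4.3 by 60 patients. Those rates come from platinum-sensitive patients taking olaparib capsules, and they count events that are first managed by supportive care, holds and dose reduction. Section 6.8.3.3 attributes fatigue to both drugs, and diarrhea has its own table. The 5 early toxicity stops among 30 platinum-resistant patients on cediranib alone (Table 4) were stops of an only drug. None of these measures how often one of two drugs would be stopped and the other continued.

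A reader might also infer a gap in the analysis. The documents do not support that. TDT uses the earliest discontinuation date when the drugs stop separately (Protocol 8.4.2, SAP 3.2.2). Combination exposure is summarized under two definitions (SAP 4.2.6), events leading to discontinuation are tabulated by drug (SAP 4.2.9), and action taken is recorded for each drug (Protocol 6.3.4). More time on one drug would make the ORR slightly less clearly that of the combination, but by an amount that cannot be stated.

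The conclusion assumes only that sites may act on Table 11 as written.

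**What to change.** 1. In Table 11 footnote a, delete *or discontinued*, so that it matches the parallel sentence in Section 6.8.
2. In Section 6.8, add one sentence: whenever one drug is permanently discontinued under Sections 6.8.1 to 6.8.4, the other may be continued only under one of the two exceptions and after the discussion with the sponsor's study physician and the Principal Investigator; stopping the causative drug is never delayed for that discussion. The last clause protects mandatory stops such as those for GI perforation and arterial thromboembolism.
3. Copy the second exception from Section 6.8 into Section 3.9 and the synopsis, so that all three state one rule.

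The cost is two words removed, one sentence added and one exception copied at the next amendment, with no new data or analysis. The downside is that investigators lose sole discretion to keep a patient on one drug after an unlisted toxicity.
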